Aim of the research

Our primary outcome is total patient-controlled analgesia (PCA) morphine sulphate (MS) consumption within seventy-two hours after surgery. Secondary outcomes include pain-intensity, measured using visual analog scale (VAS), Ramsay sedation scale (RSS), and nausea, vomiting and pruritus scale. Each of all the previous outcomes is to be recorded at 2, 8, 16, 24, 36, 48 and 72 hours after surgery.

Research Methods and Procedures

- 1- Study Design: randomized, assessor blinded, clinical trial.
- 2- Study Setting: Assuit University Hospitals, Anaesthesia and ICU department.
- 3- Study subjects:

A) Inclusion criteria:

Eligible patients are men and women aged ≥ 60 years, who are planned to undergo lower abdominal cancer surgery. Surgeries via infra-umbilical abdominal incision are considered eligible such as ovary, bladder, and colorectal surgeries.

B) Exclusion criteria:

We excluded patients with contraindications to neuraxial analgesia. The absolute contraindications are lack of consent from the patient, elevated intracranial pressure (ICP), primarily due to intracranial mass and infection at the site of the procedure (risk of meningitis). While the relative contraindications are (13,14):

- Pre-existing neurological diseases (particularly those that wax and wane, e.g., multiple sclerosis).

- Severe dehydration (hypovolemia), due to the risk of hypotension. The risk factors for hypotension include hypovolemia, age greater than 40 to 50 years, emergency surgery, obesity, chronic alcohol consumption, and chronic hypertension.
- Severe mitral and aortic stenosis and left ventricular outflow obstruction as seen with hypertrophic obstructive cardiomyopathy.
- Thrombocytopenia or coagulopathy (especially with epidural anaesthesia, due to the risk of epidural hematoma. Of note about coagulopathy, the placement of neuraxial block requires reevaluation. The American Society of Regional Anaesthesia (ASRA) publishes updated guidelines that detail timing for neuraxial anaesthesia for patients on oral anticoagulants, anti-platelets, thrombolytic therapy, unfractionated, and low molecular weight heparin. Review the latest guidelines before proceeding with the procedure.

C) Groups:

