Patients were randomized (by using a table of random numbers) to one of four groups to receive a single dose of epidural preservative-free morphine out of four doses: 0 mg (group D); 1.5 mg (Group A); 3mg (Group B) and 4.5 mg (Group D) at the beginning of surgery. A total volume of 10 mL was injected; 5 mL of bupivacaine hydrochloride 0.125% with the previously mentioned study doses of preservative-free morphine diluted in 5 mL preservative-free normal saline by the hospital pharmacist.

D) Sample Size Calculation:

The sample size will be calculated using G* Power software 3.1.9.2 considering a study power of 80% and a significance level of 0.05 to detect an effect size of 0.75 using one-

way ANOVA test/t-test. Assuming total IV-PCA morphine consumption is the main outcome variable, and the maximum total IV-PCA morphine consumption was 12 ± 16 mg while in healthy controls was 70 ± 35 mg according to previous studies (15-17), the estimated minimum required sample size, after assuming 33% dropouts, will be 88 patients (22 patients in each group).

Statistical Analysis Plan

Data will be analyzed using IBM SPSS statistics version 24 for Windows 10. A value of $P < 0.05$ was considered significant. The data will be tested for normality using the Shapiro–Wilk test. Normally distributed variables such as age and BMI are presented as the means \pm SDs and will be compared with ANOVA. When the assumption of normality was rejected, the nonparametric Kruskal–Wallis test for independent samples will be used for comparison. Significant Kruskal–Wallis test values will be Bonferroni corrected when various time points are investigated and when multiple tests are applied. For data presented as counts and percentages, a chi-squared test will be applied.

Procedure

A standardised epidural catheter insertion protocol will be followed in all the study groups. A 20-gauge, open-tip epidural catheter will be inserted into the T9-10 interspace and advanced 5 cm into the epidural space while patients are in the sitting position. A total volume of 10 mL will be injected; 5 mL of 0.125% bupivacaine hydrochloride was mixed with each of the study doses and diluted in 5 mL of preservative-free normal saline by the hospital pharmacist. We will not use

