The main strengths of this study are that it is highly reproducible and addresses the daily clinical aspects of epidural morphine in older adults. However, this study is limited by its focus on lower abdominal cancer surgeries only; additionally, it is a single centre study focused on unimodal analgesia. Therefore, the generalizability of our results is limited. All other systemic analgesics are as under-researched as epidural morphine in this age group. Therefore, further studies with larger sample on other drugs and on different types of surgeries are needed to tailor adequate multimodal pain management protocols with the least risk to the older adults. The study is also limited to clinical response and pharmacodynamics of epidural morphine in the older adults and did not investigate the pharmacokinetics, which should be examined in future studies. Due to the vulnerability of older adults, we included only ASA I and II patients to assess the balancing dose of epidural morphine versus age only. The relationship between the dose of epidural morphine and common comorbidities in this age group should also be investigated.

References:

2. Connelly P. The management of chronic pain in older persons. Vol. 46, *Journal of the American Geriatrics Society*. Blackwell Publishing Inc.; 1998. p. 635–51.
3. Schofield PA. The assessment and management of peri-operative pain in older adults. Vol. 69, *Anaesthesia*. 2014. p. 54–60.
4. Popp B P tenoy R. Management of chronic pain in the elderly: pharmacology of opioids and other analgesic drugs. In: In: IASP TF on P in the E, Ferrell B, Ferrell BA E, editors. *Pain in the elderly : a report of the Task Force on Pain in the Elderly of the International Association for the Study of Pain*. Seattle (WA): IASP Press; 1996. p. 21–4.
5. McKeown JL. Pain Management Issues for the Geriatric Surgical Patient. Vol. 33, *Anesthesiology Clinics*. W.B. Saunders; 2015. p. 563–76.

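### Cheap improvement, not an error: pre-specify adjustment of the 72-hour PCA morphine comparison for age and BMI, which the plan uses only for a baseline comparison

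*Combined protocol and SAP*

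**What the plan says.** The Statistical Analysis Plan gives one generic rule: ANOVA for normally distributed variables, Kruskal–Wallis when normality is rejected, chi-squared for counts. No sentence assigns a test to the primary outcome (total PCA morphine over 72 hours, Aim of the research). Its analysis is therefore inferred from that rule and from the Sample Size Calculation, which refers to a one-"way ANOVA test/t-test" without covariates. No covariate, regression model or stratification factor is named anywhere, and allocation is by a table of random numbers.

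Age and BMI are the only baseline variables that the analysis plan names: "Normally distributed variables such as age and BMI are presented as the means" with SDs, to be compared by ANOVA. Operation type appears only among the eligibility criteria, as examples: "such as ovary, bladder, and colorectal surgeries". Under Strength points and Limitations, the restriction to ASA I and II is explained as being "to assess the balancing dose of epidural morphine versus age only".

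**The concern.** A baseline test of age and BMI between randomised groups tells the analyst little, because any difference is due to chance by design. The same two variables, placed in the primary model, would remove whatever part of the variation in PCA use they explain and would correct for chance imbalance. The plan uses them for the first purpose and not the second.

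Chance imbalance is not rare with small arms. With about 15 evaluable patients per arm, the difference in means of a continuous covariate between two arms has a standard error of √(2/15) = 0.365 SD. A gap of 0.5 SD or more (0.5/0.365 = 1.37 standard errors) therefore occurs for a given pair with probability of about 17%.

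At stake is precision in the primary comparison. Covariates chosen after the data are seen would lack credibility, so the choice has to be made in the plan.

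**Working it through.** **Inputs from the Sample Size Calculation.** "considering a study power of 80% and a significance level of 0.05 to detect an effect size of 0.75"; 33% dropout; 88 patients in four groups of 22. **Assumptions.** Two-sided testing; two covariate degrees of freedom (q = 2); R², the share of within-group outcome variance explained by age and BMI, which the documents do not give and which is shown from 0 to 0.30.

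**1. The plan's own figure.** A two-sided t-test with d = 0.75, alpha 0.05 and 80% power needs 29 per group, or 58 for two groups. Then 58/0.67 = 86.6, so 87, or 88 as a multiple of four. The figure is reproduced, but only as a two-group total spread over four groups. After 33% dropout, 88 × 0.67 = 59 patients remain, about 15 per group. I use N = 60 (15 per group) and N = 88 (no dropout).

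**2. Starting point.** Take the non-centrality λ at which the unadjusted four-group F test has exactly 80% power: λ = 11.69 for N = 60 (3 and 56 df) and λ = 11.42 for N = 88 (3 and 84 df). This 80% is a reference level, not the trial's established power.

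**3. Effect of adjustment.** Adjustment divides the residual variance by 1/(1 − R²), removes q error df, and costs some information because covariates and arms are correlated by chance:

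λ′ = λ × [(N − 4 − q − 1)/(N − 4 − 1)] / (1 − R²), on 3 and N − 4 − q df.

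With q = 2 the bracket is 53/55 at N = 60 and 81/83 at N = 88. For example, at N = 60 and R² = 0.20: 11.69 × (53/55)/0.80 = 14.08 on 3 and 54 df.

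| R² (assumed) | N = 60: λ′ | power | N = 88: λ′ | power |
|---|---|---|---|---|
| 0 | 11.27 | 78.2% | 11.15 | 78.9% |
| 0.05 | 11.86 | 80.5% | 11.73 | 81.1% |
| 0.10 | 12.52 | 82.8% | 12.39 | 83.4% |
| 0.20 | 14.08 | 87.3% | 13.93 | 87.8% |
| 0.30 | 16.10 | 91.6% | 15.92 | 92.0% |

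Leaving out the bracket, and so counting only the lost df, would give about 82, 84, 89 and 93% for R² 0.05 to 0.30, which is too favourable.

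**4. Break-even.** The standard error is unchanged when 1 − R² equals the bracket: R² = 2/55 = 0.036 at N = 60 and 2/83 = 0.024 at N = 88. Allowing for the lost df, power breaks even at about 0.039 and 0.025.

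**5. Against the plan's effect size.** The plan does not say whether 0.75 is Cohen's d or f.
- As f, the four-group test with 15 per group already has more than 99% power, so adjustment changes nothing material.
- As d for one pair of groups (15 per group, error pooled over four groups), unadjusted power is about 52%. With two covariates the non-centrality is 0.75 × √(15/2) × √[(53/55)/(1 − R²)] on 54 df. That is 2.02 at R² = 0 (power about 51%) and 2.41 at R² = 0.30 (about 66%). Adjustment helps but does not reach 80%.

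**The case against.** The strongest case against is that nothing here is wrong. Under randomisation the unadjusted comparison is unbiased and controls the type I error, and chance imbalance is already reflected in its standard error. Adjustment is an efficiency choice whose benefit depends on an R² that the documents do not supply; below about 0.025 to 0.04 it loses a little. All of this stands, and it is why the point is an improvement only.

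Four stronger readings are tempting and not supported:

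- A reader might infer that the Background treats age as prognostic for PCA use. It speaks of the risk of side effects in older compared with younger patients. It does not address PCA consumption, or differences within a sample whose members are all 60 or over.
- A reader might infer from "to assess the balancing dose of epidural morphine versus age only" that the trial's subject is how dose response varies with age. The sentence explains the ASA restriction; the stated aim is the best dose in geriatric patients. Age as a main-effect covariate would not estimate a dose-by-age relation in any case.
- A reader might take "such as ovary, bladder, and colorectal surgeries" as a three-level variable already collected. It is an open list of examples within eligibility, with no category scheme.
- A reader might convert the gain into a fixed saving in patients. Without an R² in the documents, no such figure can be given.

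What survives the objection is the asymmetry: a small known cost against a possibly useful gain, using two variables that the plan itself names.

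**Conclusion.** The point holds as a low-cost improvement. The plan leaves age and BMI out of the primary comparison and uses them for a baseline test of little value. From a reference power of 80%, the downside if neither variable is prognostic is between 1 and 2 percentage points (80 − 78.9 = 1.1 at N = 88; 80 − 78.2 = 1.8 at N = 60). The gain is about 3 points at R² 0.10, 7 to 8 at 0.20 and 12 at 0.30.

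These figures assume a linear model, two continuous covariates and equal arms; on the rank-based route they are only a guide, with R² read on the rank scale. They do not show that the planned test is invalid, and adjustment does not repair the separate problem that 88 derives from a two-group total.

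**What to change.** In the Statistical Analysis Plan, state the primary analysis explicitly: ANCOVA of total 72-hour PCA morphine on dose group (four levels), with age and BMI as continuous covariates. If the rank-based route applies, use Quade's rank ANCOVA with the same covariates. That route is quite possible: the planning value in "the maximum total IV-PCA morphine consumption was 12 ± 16 mg while in healthy controls was 70 ± 35 mg" has an SD (16) above its mean (12) for a quantity that cannot be negative. Keep the unadjusted ANOVA or Kruskal–Wallis test as a sensitivity analysis. Present age and BMI descriptively and drop their between-group p-values.

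Add operation type only if it is recorded at baseline in categories defined beforehand. With three categories, for instance, the model would use four covariate df, and the R² at which the standard error breaks even would rise to 4/55 = 0.073 at N = 60 or 4/83 = 0.048 at N = 88.

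The cost is a few sentences in the plan, two error degrees of freedom and the small loss of power stated above if the covariates prove uninformative. For age and BMI no new data are needed. The wording should be fixed before outcome data are examined.

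### The multiplicity correction is attached only to Kruskal–Wallis results, so ANOVA and chi-squared results at the same seven times go uncorrected

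*Combined protocol and SAP*

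**What the plan says.** Under Aim of the research, the primary outcome is total patient-controlled morphine use over 72 hours. The secondary outcomes are pain on a VAS, the Ramsay sedation score, and a nausea, vomiting and pruritus scale. Each outcome "is to be recorded at 2, 8, 16, 24, 36, 48 and 72 hours after surgery".

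The Statistical Analysis Plan then routes the data by type:

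- The general rule is that a P value below 0.05 "was considered significant. The data will be tested for normality using the Shapiro–Wilk test".
- Normally distributed variables, with age and BMI as the examples, go to ANOVA. No correction is stated.
- If normality is rejected, Kruskal–Wallis is used, and significant "test values will be Bonferroni corrected when various time points are investigated and when multiple tests are applied".
- Categorical data get a separate sentence: "For data presented as counts and percentages, a chi-squared test will be applied". No correction is stated.

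The plan names no repeated-measures model, summary over time or key time point. It does not say how many tests the Bonferroni divisor counts, or whether comparisons between pairs of groups are among them.

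**The concern.** The reason for correcting is that one outcome is examined at several times. That reason is the same for every test statistic, yet the written rule follows the statistic. VAS at 24 hours could be corrected because Shapiro–Wilk rejected normality there, while VAS at 36 hours is not corrected because it did not. Nausea would be corrected as a score but not as a percentage of patients.

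The Background says the trial seeks the best pain control with the fewest adverse effects. The choice between doses will therefore lean on these secondary comparisons. A single nominally significant time among many, on a branch with no correction, could be read as a dose difference.

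**Working it through.** **Inputs from the documents.** Seven times (Aim of the research); four groups; 88 patients, so 88/4 = 22 per group (Sample Size Calculation); threshold 0.05; planned dropout 33%, so 88 × 0.67 = 58.96, or about 15 per group. The plan gives no family-wise error rate to reproduce. Its one related figure, 88, can be recovered as a two-group, two-sided t-test with d = 0.75: 29 per group, 58 in all, 58/0.67 = 86.6, rounded up to four equal arms of 22. Sample size is otherwise a separate matter.

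**Assumptions, not in the documents.** Within-patient correlation between times of 0.3 to 0.7; symptom rates of 10–30%; a symptom scored as present or absent at each time.

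**Step 1: upper guide, independent tests.** The chance of at least one false positive in m tests at 0.05 is 1 − 0.95^m.

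- m = 7: 1 − 0.95^7 = 30.2%
- m = 3 × 7 = 21: 1 − 0.95^21 = 65.9%

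**Step 2: allow for correlation.** Trials were simulated with no dose effect (4,000 per setting). The table gives the percentage with at least one P value below the limit.

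| Analysis, no true difference | Correlation 0.3 | 0.5 | 0.7 |
|---|---|---|---|
| ANOVA at 7 times, uncorrected, 22 per arm | 26.7 | 22.7 | 19.3 |
| ANOVA at 7 times, uncorrected, 15 per arm | 27.8 | 24.4 | 18.9 |
| Chi-squared, 1 symptom at 7 times, rate 30%, uncorrected, 22 per arm | 28.4 | 26.5 | 23.4 |
| Chi-squared, 3 symptoms at 7 times, rate 30%, uncorrected, 22 per arm | 61.3 | 58.6 | 54.6 |
| Kruskal–Wallis at 7 times, each at 0.05/7 = 0.0071, 22 per arm | 3.4 | 3.5 | 3.1 |

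Lower symptom rates move the chi-squared figures only a little. Over the settings tried the ranges are 19–28% (ANOVA), 21–28% (one symptom) and 53–61% (three symptoms).

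**Step 3: what one common rule would do.** Holm compares the smallest of seven P values with 0.05/7 = 0.0071, the next with 0.05/6 = 0.0083, and so on up to 0.05. It holds the chance of any false positive within the family to 5% or less if each test is itself valid, and it never rejects less than Bonferroni. With a family for each outcome, the bound across three symptoms is 3 × 5% = 15%.

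**The case against.** The strongest reply is that the uncorrected branches may hardly be used. ANOVA is illustrated only by age and BMI. Ramsay scores are ordinal and VAS is bounded, so both may well fail Shapiro–Wilk. The symptoms are described as a scale, and if analysed as scores they too go to Kruskal–Wallis. All of this concerns secondary outcomes, since the primary is one total at 72 hours. Separate testing at each time is also inferred: the plan names only tests of independent samples and mentions time points, but never says outright that each time is tested.

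Most of this stands, and it makes the percentages conditional. It does not remove the defect. The text still lets a data-dependent test decide whether a result is corrected, and it leaves any symptom reported as a count with no correction. Nothing in the plan gives a reason for treating the branches differently.

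A reader might also infer that the Kruskal–Wallis branch is under-powered and that a time-weighted mean should replace the seven tests. The documents do not support that, because they give no shape for the effect over time. Take a VAS with SD 2, 22 per arm, full-size shifts of 1.5, 1.0, 0.5 and 0, and correlation 0.3 to 0.7:

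- Effect constant over all seven times: at least one Bonferroni-significant time in 54–70% of trials, against 67–90% for the time-weighted mean.
- Effect confined to early readings: 39–54% against 9–12%.
- Effect that decays: 20–28% against 9–17%.

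The ranking reverses. The documents do not settle the shape: the Groups section describes a single dose at the start of surgery, while the Procedure repeats it at 24 and 48 hours, and these must be reconciled. The first reading is at 2 hours, so the observed area spans 72 − 2 = 70 hours. Trapezoid weights give the 2-hour reading 3/70 = 4.3%, and the 48- and 72-hour readings together (18 + 12)/70 = 43%. An average of Ramsay scores could hide a brief episode of deep sedation.

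**Conclusion.** The point holds as an inconsistency in the correction rule. The plan has decided that several times and several tests need correcting, and then applies that decision to one of its three test types. Where the other two are used, the chance of at least one false positive is about 19–28% for one scale by ANOVA, 21–28% for one binary symptom, and 53–61% for three, against 3.1–3.5% on the corrected branch.

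These figures rest on assumed correlations and symptom rates, and on all seven times going down the same uncorrected branch. They should not be read as the error rate of the plan as a whole, because results sent to Kruskal–Wallis are corrected. They do not touch the primary analysis. Nor do they show that the Kruskal–Wallis branch lacks power or that a summary over time is required. The change is worth making before analysis, but it does not threaten the main result.

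**What to change.** Replace the Bonferroni sentence with one rule that does not depend on the test. For example:

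*For each secondary outcome, the overall four-group comparisons at the seven recorded times form one family. P values within a family are adjusted by Holm's method at 0.05, whether they come from ANOVA, Kruskal–Wallis or chi-squared.*

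The SAP should also state how comparisons between pairs of groups are handled (4 × 3/2 = 6 pairs). If the sponsor wants control across outcomes as well, it should name the wider family.

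Two options can be added:

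- Test any occurrence of each symptom over the 72 hours once. That replaces 21 symptom tests with 3.
- Use a summary measure for VAS, with its window and its handling of missing scores fixed in advance.

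The cost is SAP wording; no new data are needed. The downside is that ANOVA and chi-squared results become harder to call significant, adverse effects included. As a guide, with an assumed 0 to 0.75 SD trend over the doses and 22 per arm, power at one given time by Kruskal–Wallis falls from about 53% at 0.05 to about 23% at 0.05/7; Holm recovers some of this when several times differ. The report should therefore show estimates with unadjusted intervals at each time for every outcome, so that a possible harm stays visible whether or not its adjusted P value is below 0.05.
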